
Background & Significance

Liver transplantation has become the standard treatment for many metabolic and end-stage liver diseases but remains one of the most complex abdominal surgeries. As such, liver transplantation is a growing field with more than 7,500 liver transplants performed in the US in 2016. Many of the complications associated with liver transplantation that lengthen hospitalization are related to postoperative pain control. Opioid medications are the standard of care and foundation for post-liver transplantation pain control and are associated with many side effects including prolonged post-operative ileus, delayed return of bowel function leading to a longer interval before reinitiating enteral nutrition, nausea, and extended time to getting up and out of bed.

Postoperative pain management has been a challenge since the field of surgery was invented. Nonetheless, acupuncture has been around since ancient times to help control pain of many types, as have opioid-based medications. Modern scientific approaches have validated the use of acupuncture, electroacupuncture, and transcutaneous electric acupoint stimulation (TEAS) for reducing pain scores and opioid use after surgery. A meta-analysis by Wu and colleagues found that acupuncture and related techniques caused lower utilization of opioid pain medications in the postoperative setting, with the most significant opioid reduction seen in patients treated with TEAS. The stimulation of the external ear may have particular benefit. A study by Greif et al. evaluated electrical stimulation to a point 3cm

anterior to the auricular tragus, a site often used by German anesthesiologists to reduce pain requirements. They found that those patients having auricular stimulation were able to tolerate more painful sensory stimulation before needing rescue narcotics.

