Postoperative ileus will be measured by need for nasogastric decompression for >48 hours; again, these events are routinely documented in the medical record as part of routine medical care. Time to sitting up in a chair and time to walking will be determined based on patient symptom surveys. Diet will be advanced as determined by the primary care team. Once the patients are able to tolerate oral intake, oral opioid medications will be started as needed. Escalation of this oral pain regimen will be noted but will not warrant exclusion from the study. Patients needing additional pain control with regional anesthesia techniques will be excluded from the study at that time. Patients will be discharged from the hospital once discharge criteria are met as determined by the treating physician. All patients will receive a standard narcotic pain medication prescription at discharge. The patients will receive an information sheet upon discharge with study and device information as well as contact information for study team members.

All patients will receive a phone call on device day 30 by the study coordinator, PI, or co-PI. At this time, the patients will again be asked to complete the numerical pain scale, BAI, symptom survey, and PONV score via telephone, and will be asked if he or she is still requiring narcotic pain medication, or if a refill of the narcotic pain medication was needed.

Device Removal

The study investigators, PI, or co-PI will remove the device after 120 hours of stimulation. The date and time of device removal will be recorded. If the patient is at home after 5 days, then the patient will be asked to remove it and to bring it to the next clinic appointment for proper disposal. If a device falls off completely, it should not be reapplied. If individual electrodes are dislodged, they can be reapplied with household adhesive tape. If a patient requests withdrawal from the study or removal of the device before the 5-day device life has expired, time of removal will be recorded.

Risk/Benefit Assessment

Overall risks/ discomforts involved are very minimal – Rare (event rate 1% - < 5%)

Possible risks/discomforts may involve:

Discomfort upon insertion of the electrodes for < 5 minutes - Rare (event rate 1% - < 5%)

Discomfort at the lead placement site > 5 minutes - Rare (1 % - < 5%)

Bleeding at the electrode site if the neurovascular bundle is penetrated - Rare (event rate 1% - < 5%)

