Localized discomfort if the electrodes should become dislodged during the wearing of the device - Rare (event rate 1% - < 5%)

Localized dermatitis - Rare (event rate 1% - < 5%)

Drop in blood pressure - Rare (event rate 1% - < 5%)

Syncope (fainting) - Rare (event rate 1% - < 5%)

Adverse effects to supporting personnel

Skin piercing with percutaneous needles - Rare (event rate 1 % - < 5%)

There are numerous, possible direct and long-term benefits to the subjects in this study. The results of this study may provide important insights to the medical field regarding a new, non-pharmacologic therapy that could improve pain control and quality of life for patients undergoing liver transplantation. If effective, a significant decrease or prevention in post-operative opioid use would be a major breakthrough in healthcare. This treatment would then have the potential to be extrapolated to other post-operative settings and populations.

Data Analysis & Statistical Considerations

This randomized study and the subjects will be randomized 1:1 ratio to the treatment groups. The primary efficacy endpoint is opioid usage after surgery in the two groups, and the related secondary endpoint is pain score in the two groups at the end of surgery. Normality possible transformations to attain normality of these variables will be assessed. These variables will be analyzed using either a two-sample t-test or non-parametric Wilcoxon test, depending on whether the outcomes are normal or non-normal. Analysis will be conducted under Intent-To-Treat (ITT), and any missing outcome will be imputed under missing at random (MAR) using multiple imputation methods. In addition, complete case analysis will be conducted. Continuous outcomes, adjusted for covarites, will be examined using regression analysis. Significance of the results will be examined at a two-tailed 0.05 alpha level.

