Other secondary outcomes are: postoperative nausea and vomiting, postoperative ileus, postoperative immobility, length of hospital stay, incidence of ileus and time to return of bowel function, time to physical function, complications, and re-hospitalization. Continuous variables here will be analyzed using two-sample t-test or non-parametric Wilcoxon test, depending on whether the variables are normal or non-normal; categorical variables will be compared using chi-squared tests; time to event analysis will be examined using Kaplan-Meier curves. In addition, adjusted continuous outcomes will be examined using regression analysis; adjusted dichotomous outcomes will be examined using logistic regression; and adjusted time-to-event analysis will be examined using Cox proportional models. These analyses are exploratory, and significance will be assessed with and without adjusting for multiple testing.

Adverse events of this trial are infections and complications. Rates of infections and complications between the groups will be examined using Fisher's exact test or Chi-squared test.

Power: At the least (without any research funding) 25 subjects each will be randomized to the treatment groups. At alpha = 0.05 and 80% power and 25 subjects randomized to treatment groups, we should be able to observe effect size of about 0.81 between the two groups on the outcome of opioid usage; if we secure external funding, we should be able to randomize at least 32 subjects to each of the treatment groups. With 32 subjects in each groups, at alpha = 0.05 and 80% power, we should be able to observe effect size of 0.71 between the two groups. If we assume a 20% dropout rate, with the above sample sizes, we would observe effect sizes between .69 and 0.80 (Cohen, 1988).

Analysis will be conducted using statistical software SAS 9.4 (SAS Institute, Inc., Cary, NC).

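### The adverse-event definition names none of the seven listed patient risks of the device and leaves complications undefined, so the plan as written yields no incidence for any of them

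*Combined protocol and SAP*

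**What the plan says.** Data Analysis & Statistical Considerations defines the safety outcome in one sentence, "Adverse events of this trial are infections and complications", and gives its analysis in the next: "Rates of infections and complications between the groups will be examined using Fisher's exact test or Chi-squared test". Neither category is defined. The same section uses the second term again in its list of other secondary outcomes, which ends "time to physical function, complications, and re-hospitalization".

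The Risk/Benefit Assessment lists seven risks to the patient from the device:

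- discomfort at insertion lasting under 5 minutes
- discomfort at the lead site beyond 5 minutes
- bleeding at the electrode site
- discomfort from a dislodged electrode
- localized dermatitis
- a drop in blood pressure
- syncope

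Each is rated rare, at 1% to under 5%. An eighth item, needle injury, concerns staff.

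Under Study Interventions, the paragraph on screen failures lets device-arm subjects keep the device on for the full 120 hours after screen failure. It also says that follow-up assessments are not done in screen failures.

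**The concern.** The device puts needles in the ear of liver-transplant patients for up to five days, and the protocol looks ahead to use in other surgical populations. Readers will want to know how often each foreseen device harm occurred. The document foresees seven such harms in one section, and its safety definition and analysis in another section mention none of them.

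If the statistical section is followed as written, the report will contain rates of infection and of complications by arm. It need not contain a count for electrode-site bleeding, dermatitis, lead-site discomfort or syncope. The single planned method is a comparison between arms, which does not suit an event that can occur only where a device is worn.

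**Working it through.** **Step 1. Set the listed risks against the definition.** The plan gives no safety figure to reproduce; its power figures concern opioid use, and only their sample sizes are used here.

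| Listed patient risk | Possible in controls? | Fit with infections and complications |
|---|---|---|
| Insertion discomfort, under 5 min | No | Poor |
| Lead-site discomfort, over 5 min | No | Poor |
| Electrode-site bleeding | No | Possible, if complications is read broadly |
| Discomfort from dislodged electrode | No | Poor |
| Localized dermatitis | No (taken as at the device site) | Poor |
| Drop in blood pressure | Yes | Possible, but pooled |
| Syncope | Yes | Possible, but pooled |

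What complications means has to be inferred. Background & Significance uses the word for the operation: "Many of the complications associated with liver transplantation that lengthen hospitalization are related to postoperative pain control". If that sense carries over, all seven risks are left uncounted. If the word is read broadly, three of the seven enter a pooled category dominated by a major abdominal operation, and four remain poorly covered. Neither reading gives a rate for any one device risk.

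**Step 2. What the planned test can show for an electrode-site event.** Inputs: 35 per group (Selection of Subjects), 25 or 32 per group (power paragraph), and two-sided alpha 0.05. With x events in the device arm, none in controls and n per arm, the two-sided Fisher p-value is 2 × C(n, x) / C(2n, x).

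| n per arm | x = 5 | x = 6 |
|---|---|---|
| 25 | 0.0502 | 0.0223 |
| 32 | 0.0528 | 0.0242 |
| 35 | 0.0536 | 0.0248 |

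Six events are therefore needed at every size. If the true rate were 5%, the top of the documents' range, the binomial chance of 6 or more device-arm events is 0.1% (n = 25), 0.5% (n = 32) and 0.7% (n = 35).

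The plan also allows a chi-squared test. Without continuity correction its statistic is 2n·x / (2n − x). For n = 35 this is 70 × 3 / 67 = 3.13 at x = 3 and 70 × 4 / 66 = 4.24 at x = 4, so it passes the critical value of 3.84 at 4 events. The same holds for n = 25 (150 / 47 = 3.19, then 200 / 46 = 4.35) and n = 32 (192 / 61 = 3.15, then 256 / 60 = 4.27). At 4 events the expected count in each event cell is 4 / 2 = 2, too small for the chi-squared approximation to be relied on, so Fisher's test is the relevant one. With either test, the control rate is zero by design and the p-value does not describe the harm.

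**Step 3. What an exact interval gives instead.** With zero events in n patients, the two-sided exact 95% upper limit is 1 − 0.025^(1/n).

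- n = 25: 1 − 0.025^(1/25) = 13.7%
- n = 32: 1 − 0.025^(1/32) = 10.9%
- n = 35: 1 − 0.025^(1/35) = 10.0%

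**Step 4. Look for capture elsewhere.**

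- The daily symptom sheet is described as covering pain, nausea, vomiting and mobility.
- One domain of the APS-POQ-R concerns side effects of treatment, with no device-site item described.
- Patients are told to report discomfort that persists or worsens after placement, but no recording is stated.
- The time of an early removal is recorded, but no reason is asked for.
- The day-30 call lists pain, anxiety, symptom and nausea measures and narcotic use.

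None of these is linked to the safety analysis.

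**The case against.** The strongest reply is that complications is an open term. Nothing in the document excludes device events from it, and an infection at an electrode site would be an infection. That stands. A reader might infer that the plan confines adverse events to two categories and places every device risk outside them. The text does not go that far: it supports only that inclusion of bleeding, a drop in blood pressure or syncope cannot be determined. Nor does it label complications an efficacy outcome, so its place among the secondary outcomes does not settle its meaning.

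A second reply is that some signals of harm exist, as Step 4 shows, so it would be too strong to say that the trial could learn nothing about device harm. That also stands, but partial signals with no link to an analysis are not an incidence. The visit timeline in Table 1 is not in the text available for this review, so the point rests on the stated definition and analysis and makes no claim that nothing is collected.

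A third reply concerns the 1% to under 5% figures. A reader might infer that the trial should test them. They belong to a risk disclosure, no objective is to verify them, and 25 to 35 device patients could not confirm a rate below 5% however the events were defined.

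Finally, the plan speaks of rates, which implies figures by arm, and Fisher's or a chi-squared test is reasonable for the two categories it names. The limitation in Step 2 applies to electrode-site events.

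**Conclusion.** The point holds as an undefined term combined with an omission. The definition names none of the seven patient-level device risks, and under a narrow or a broad reading of complications the plan gives no incidence for any of them. For the five electrode-site risks, the between-group test would need at least 6 events against 0, and the chance of that is below 1% even at a 5% rate.

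This rests on three assumptions: localized dermatitis is a device-site event, controls wear no device, and all 25 to 35 device patients are observed. The last is optimistic, since screen-failed subjects may wear the device without follow-up assessments. The point should be dealt with before analysis. It bears on what the trial can say about harm and leaves the primary comparison of opioid use untouched.

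**What to change.** 1. Define complications, and state whether it means surgical events, device events or both.
2. Name the seven patient risks in the Risk/Benefit Assessment as adverse events. Record them at existing contacts from device placement to removal, and at the day-30 call. For events possible in both arms, record them over the same period in controls.
3. Include screen-failed subjects who keep wearing the device in this recording.
4. Report electrode-site events in the BRIDGE arm as counts with exact 95% intervals, including when the count is zero.
5. Compare between groups only the events that both arms can have: a drop in blood pressure, syncope, infections and complications as defined.

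The cost is a revision of the plan's wording, a short checklist at contacts that already take place, and slightly more data entry, including some for screen failures. Treatment and sample size do not change. The intervals will be wide and should be presented as such.

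### The detectable effects given for 20% dropout (0.69 to 0.80) are smaller than the plan's own no-dropout values (0.71 and 0.81); if dropouts supply no outcome data they should be about 0.80 and 0.91

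*Combined protocol and SAP*

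**What the plan says.** All the statements are in Data Analysis & Statistical Considerations; the effect sizes are in its Power paragraph.

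- Primary endpoint: "The primary efficacy endpoint is opioid usage after surgery in the two groups".
- Test: "These variables will be analyzed using either a two-sample t-test or non-parametric Wilcoxon test", the choice depending on normality.
- Level: "Significance of the results will be examined at a two-tailed 0.05 alpha level".
- 25 per group, 80% power: "we should be able to observe effect size of about 0.81 between the two groups on the outcome of opioid usage".
- 32 per group: "With 32 subjects in each groups, at alpha = 0.05 and 80% power, we should be able to observe effect size of 0.71".
- With dropout: "If we assume a 20% dropout rate, with the above sample sizes, we would observe effect sizes between .69 and 0.80".
- Missing data: the analysis is by intention to treat, and "any missing outcome will be imputed under missing at random (MAR) using multiple imputation methods". The plan then adds: "In addition, complete case analysis will be conducted".

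The dropout sentence does not say which end of its range belongs to which sample size, or whether dropouts' opioid use is assumed known. No one-sided test is declared anywhere.

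**The concern.** The dropout sentence refers back to 25 and 32 per group, yet its range is lower at both ends than the values just given for those groups without loss: 0.69 against 0.71, and 0.80 against 0.81. At a fixed test, alpha and power, the detectable effect rises as the number of evaluable patients falls. The three sentences therefore cannot all be right.

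This is the plan's only statement of what the trial can detect on its primary endpoint once patients are lost, and the error makes the trial look more sensitive than it is. Someone interpreting a null result, or planning a follow-on study from this paragraph, would credit the trial with 80% power at effects where it has less.

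**Working it through.** **Inputs.** Two-tailed alpha 0.05, 80% power, two-sample t-test, 1:1 allocation, 25 or 32 randomised per group, 20% dropout. All come from Data Analysis & Statistical Considerations.

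**Method.** With n evaluable per group and standardised difference d, the t statistic has 2n − 2 degrees of freedom and noncentrality d × √(n/2). The detectable effect is the d at which two-sided power equals 0.80, solved numerically. The normal approximation, d ≈ (1.960 + 0.842) × √(2/n), serves as a rough check.

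**Step 1: the plan's no-dropout figures.**

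- n = 25: d = 0.809 (plan: about 0.81). Power at 0.81 is 80.1%.
- n = 32: d = 0.711 (plan: 0.71). Power at 0.71 is 79.8%.

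Both reproduce, so the two-sided t-test is the basis of these sentences.

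**Step 2: 20% dropout, dropouts contributing no outcome data.**

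- 25 × 0.80 = 20 per group: d = 0.909 (normal approximation 2.802 × √(2/20) = 0.886).
- 32 × 0.80 = 25.6 per group: d = 0.799 (normal approximation 0.783). Rounded up to 26 per group: d = 0.792.

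The range is about 0.80 to 0.91. The stated range of 0.69 to 0.80 does not reproduce.

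**Step 3: power at the stated effects after that loss.**

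- d = 0.80, n = 20: 69.3%.
- d = 0.69, n = 25.6: 67.7%; n = 26: 68.4%.

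An effect of 0.69 at 80% power needs 33.96, that is 34, evaluable per group. That exceeds both 25 and 32 before any loss.

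**Step 4: dependence on what is known about dropouts.** The documents do not say how much of the dropouts' opioid use will be available.

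| Share of dropouts with known opioid use | Evaluable per group (of 25 / of 32) | Detectable effect (25 / 32) |
|---|---|---|
| none | 20 / 25.6 | 0.909 / 0.799 |
| half | 22.5 / 28.8 | 0.855 / 0.751 |
| all | 25 / 32 | 0.809 / 0.711 |

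In the last row, power at the stated effects is 79% (0.80 with 25) and 78% (0.69 with 32). In every row the stated pair is too small.

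**Step 5: other readings.**

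- *The two ends pair differently.* A value of 0.80 is right for 32 randomised with 20% loss. The 25-per-group value (0.91) is then missing, and 0.69 fits neither scenario.
- *25 and 32 are completers.* The effects stay at 0.81 and 0.71.
- *35 per group (Selection of Subjects).* The effect is 0.68 with complete data, and 0.76 with 35 × 0.80 = 28.
- *Wilcoxon test.* Taking its efficiency relative to the t-test as 0.955 (an assumption, not in the plan), the post-dropout effects are about 0.93 and 0.82, further from the stated pair.
- *One-sided 0.05 test.* n = 20 gives 0.801; n = 26 gives 0.699 by the t-test and 0.690 by the normal approximation. This is close to the stated pair and may be how it arose. The documents do not confirm it, and it conflicts with the declared two-tailed level.

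**The case against.** The strongest objection is that 0.80 and 0.91 depend on dropouts contributing nothing. The main analysis is intention-to-treat with multiple imputation, and complete-case analysis is an addition. If opioid use were known for everyone, power at the stated effects would fall short of 80% by only 1 to 2 points, not 11 to 12. This stands as a point about size: the direction of the error is certain, its size is conditional. It does not rescue the sentence, because imputation cannot make the trial more sensitive than complete data would, and complete data give 0.81 and 0.71. Loss of outcome data is also plausible. Patients who miss the visit 2 assessments become screen failures without follow-up assessments (Study Interventions, Screen failures), and those given regional anaesthesia are excluded (Intraoperative and Postoperative Protocol). Nothing says their opioid use will still be collected.

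Second, 25 and 32 are described as minimum numbers, and Selection of Subjects anticipates 35 per group, so 34 evaluable per group is attainable if nobody is lost. That is true, but the sentence concerns the 25 and 32 already named and assumes 20% loss. Even 35 with that loss gives 0.76.

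Third, little depends on the sentence. Enrolment in the Power paragraph is driven by funding, no target effect is justified, and Background & Significance calls the study a pilot. This is fair and limits the weight of the point. It does not make the figures right.

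**Conclusion.** The concern holds. The dropout sentence contradicts the two sentences before it, and no reading consistent with the declared two-tailed 0.05 test reproduces its range. If dropouts contribute no primary-outcome data, the detectable effects are about 0.91 (25 randomised per group) and 0.80 (32 randomised per group), and power at the stated effects is about 69% and 68%. If all dropouts' opioid use were known, the no-dropout values of 0.81 and 0.71 would apply.

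These figures rest on the t-test, equal loss in the two groups and 80% power. The point should be fixed as a correction to a stated figure that errs in the trial's favour. It is not a fault in the design.

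**What to change.** Replace the dropout sentence in the Power paragraph with:

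> With 20% dropout, assuming dropouts contribute no primary-outcome data, the detectable effect sizes at two-sided alpha 0.05 and 80% power are about 0.91 (25 randomised per group) and 0.80 (32 randomised per group).

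If the sponsor expects to obtain opioid use for some or all dropouts, the sentence should say so and give the matching values from the table above. The figures for 35 per group (0.68 with complete data, 0.76 with 20% dropout) could be added so that the paragraph also covers the enrolment anticipated in Selection of Subjects.

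The cost is one sentence of wording and a less favourable stated sensitivity. No extra patients are needed.
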